7.6.4 Vital Signs

Vital sign measurements, including systolic and diastolic blood pressures, heart rate, respiratory rate, and body temperature, will be presented in a data listing. The values meeting the toxicity grading criteria will be flagged in the data listing. The abnormalities meeting the toxicity grading criteria (Grade 2 or higher) in any vital sign measurement will be listed separately. If a participant has a vital sign result with Grade 2 or higher

Date Issued: 25May2021

abnormality at any post vaccination visit, then all results for that participant and vital sign measurement will be presented in the listing.

Observed values and changes from Baseline for all vital sign measurements will be summarized at each scheduled visit by treatment groups as defined in Section 7.1. Shift from baseline in the toxicity grades to the worst post-vaccination result will be summarized by treatment group and vaccination (first or second).

Incidence of vital sign abnormalities of Grade 2 or higher after any vaccination and through 7 days after any vaccination will be summarized by treatment group.

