3.5.9 Vital Sign Measurements

Vital sign measurements will include systolic and diastolic blood pressure, heart rate, respiratory rate, and body temperature (preferred route is oral). The participant will be seated for at least 5 minutes before all measurements are taken. Vital signs will be measured at the time points indicated in the Schedule of Events (Table 5). On Visits Day 1 and Day 29, vital

sign measurements will be collected once before vaccine administration and at least 1 hour after vaccine administration (before participants are discharged from the clinic).

When procedures overlap and are scheduled to occur at the same time point, the order of procedures should be vital sign measurements and then the blood collection.

If any of the vital sign measurements meet the toxicity grading criteria for clinical abnormalities (Table 6) of Grade 3 or greater, the abnormal value and grade will be documented on the AE page of the eCRF (unless there is another known cause of the abnormality that would result in an AE classification). The investigator will continue to monitor the participant with additional assessments until the vital sign value has reached the reference range, the vital sign value at baseline, is considered stable, or until the investigator determines that follow-up is no longer medically necessary.

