Blood sample collection for vaccine-induced immunogenicity assay ^k	-	X^{l}	_	-	ı	X ^l	_	_		X	_	X	-	X
Post-vaccination SC ^m	_	_	X	X	_	_	X	X	_	_	X	_	X	_
Return and review diary card	_	_	_	_	X	X	_	_	X	X	_	1	_	_
Record unsolicited AEs	_	X	X	X	X	X	X	X	X	X	_	-	_	_
Record SAEs, MAAEs, and AEs of special interest ⁿ	_	X	X	X	X	X	X	X	X	X	X	X	X	X

Page 90

- Abbreviations: –, not collected; AE, adverse event; C, clinic visit; AE, adverse event; AESI, adverse event of special interest; ELISA, enzyme-linked immunosorbent assay; EOS, end of study; IgG, immunoglobulin G; IgM, immunoglobulin M; MAAE, medically attended adverse event; NA, not applicable; SAE, serious adverse event; SC, safety telephone call; SOE, schedule of events.
- ^a Unless consent is withdrawn, a participant who discontinues from receiving the second dose of study vaccine will remain in the study and complete all safety and immunogenicity procedures required through 1 month after the last vaccination received per the SOE (i.e., up to Day 29 for subjects receiving only the first dose of vaccine). Subjects will then enter the 12-month Long-Term Follow-up Phase per the SOE.
- Vital sign measurements will include systolic and diastolic blood pressure, heart rate, respiratory rate, and body temperature. Oral temperature is preferred route. The participant will be seated for at least 5 minutes before all measurements are taken. Vital sign measurements will be collected once before dose administration and at least 1 hour after dose administration (before participants are discharged from the clinic) on Visits Day 1 and Day 29. When procedures overlap and are scheduled to occur at the same time point, the order of procedures should be vital sign measurements and then the blood collection.
- A full physical examination, including height and weight (and body mass index calculation), will be performed at screening (Section 3.5.10); symptom-directed (targeted) physical examinations will be performed at all other scheduled time points. Interim physical examinations will be performed at the discretion of the investigator. Investigator may perform targeted physical examinations at Month 7 and Month 13 at their discretion. A physical examination of the arm that was vaccinated and the associated lymph nodes should be evaluated before each vaccination and at 7 days post-vaccination.

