- Study Day on or after the date of the first vaccination but before the second vaccination (if applicable) will be calculated as: date of assessment/event date of the first vaccination + 1;
- Study Day after the date of the second vaccination will be calculated as: date of assessment/event date of the second vaccination + 1; if Study Day is on the same day as the second vaccination, date and time will be compared with the second vaccination date and time. If it is prior to the second vaccination, then study Day is calculated as: date of assessment/event date of the first vaccination + 1; If it is after the second vaccination then Study Day is calculated as: date of assessment/event date of the second vaccination + 1.

For GMT calculation, antibody values reported as below LLOQ will be replaced by $0.5 \times LLOQ$. Values that are greater than the upper limit of quantification (ULOQ) will be converted to the ULOQ. Missing results will not be imputed.

Date Issued: 25May2021

The following timeframes will be defined for reporting safety data in this study:

- Vaccination: First vaccination on Day 1 to 28 days after last vaccination. If a participant receives two vaccinations, this stage starts at the first vaccination on Day 1 and continues through the 28th Day after the 2nd vaccination.
- Within 28 days of vaccination: Consists of all periods that begin with a vaccination and continue through the 28th Day after the vaccination. This is a subset of the vaccination stage. If a participant receives two vaccinations, this stage includes the two 28-Day periods that begin after each vaccination.
- Overall: Begins at the first vaccination on Day 1 and continues through the final safety call.

Analysis sets for the various analyses are defined in Section 6.

The 95% confidence interval (CI) for percentage will be obtained from SAS procedure of Proc Freq using Clopper-Pearson method. The 95% CI for GMT will be calculated based on the t-distribution of the log-transformed values then back transformed to the original scale for presentation.

Expected visit windows for all study assessments are detailed in Appendix A.

All analyses will be conducted using SAS Version 9.4 or higher.

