10.1 Appendix A Analysis Visit Windows for Safety and Immunogenicity Analysis

Table 3 Visit Window Mapping Rules

| Table 3 Visit Window Mapping Rules | | |
|---------------------------------------|--|----------------------------|
| Labs (Hem | atology, Chemistry, and Coagulation) and | l Vital Signs |
| Visit | Target Study Day | Visit Window |
| Day 1 | Date of First Vaccination (1) | Pre-dose |
| Day 1, 1 hour postdose – Vitals only | 1 | ≥ 1 hour post-dose |
| Day 8 - Labs only | 8 | [8,11] |
| Day 29 | Date of Second Vaccination (29) | [29,36] |
| Day 29, 1 hour postdose – Vitals only | 29 | ≥ 1 hour post-dose |
| Day 36 - Labs only | 36 | [36,39] |
| Day 57 (Month 2) – Labs only | 57 | [50,64] |
| | Adverse Events | |
| Stage | Vaccination | Target Time Frame |
| Vaccination | All | [1, 57] |
| Short-Term Follow-up | First | [1,29] |
| | Second | [29,57] |
| Long-Term Follow-up | First | NA |
| | Second | [57, Month 12 Safety Call] |
| Overall | All | [1, Month 12 Safety Call] |

Protocol mRNA-1893-P101

| Immunogenicity | | | | | |
|-------------------------------------|-------------------------------|------------|--|--|--|
| Visit Target Study Day Visit Window | | | | | |
| Day 1 | Date of First Vaccination (1) | Pre-dose | | | |
| Day 29 | 29 | [29,36] | | | |
| Day 57 (Month 2) | 57 | [50,64] | | | |
| Month 7 | 196 | [182,210] | | | |
| Month 13 | 364 | [343, 385] | | | |

Protocol mRNA-1893-P101

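### The vital-sign shift table by vaccination sets the worst of two scheduled readings after dose 1 against a single scheduled reading after dose 2

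*SAP*

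**What the plan says.** SAP 7.6.4 specifies two graded summaries of vital signs. The first is split by vaccination: "Shift from baseline in the toxicity grades to the worst post-vaccination result will be summarized by treatment group and vaccination (first or second". The second is by treatment group only: "Incidence of vital sign abnormalities of Grade 2 or higher after any vaccination and through 7 days after any vaccination". The same section also summarises observed values and changes from baseline at each scheduled visit.

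The Schedule of Events (Protocol Appendix 1, Table 5) marks vital signs at Screening, Day 1 and Day 29 and nowhere else. Its footnote sets the timing on the two vaccination days: "Vital sign measurements will be collected once before dose administration and at least 1 hour after dose administration". Protocol 3.5.9 gives the same rule. SAP Appendix A, Table 3 agrees. Its later post-dose rows read "Day 8 - Labs only", "Day 36 - Labs only" and "Day 57 (Month 2) – Labs only", and it lists the 1-hour readings on Day 1 and Day 29 as separate rows for vital signs.

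SAP 7.1 says how an assessment made on the day of dose 2 is placed: "If it is prior to the second vaccination, then study Day is calculated as" a count from the first vaccination. SAP 7.6.3 states that scheduled and unscheduled assessments both count towards the worst laboratory value. SAP 7.6.4 has no such sentence for vital signs.

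**The concern.** A worst-value summary depends on how many values it is taken over. A table laid out by first and second vaccination invites the reader to ask whether abnormalities rise with the second dose. If the first column is the worse of two readings and the second column is one reading, the first column is raised by ascertainment alone. A true rise after dose 2 could then be reduced or hidden.

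The wording used for vital signs closely matches that used for laboratory tests in SAP 7.6.3. It suits laboratory tests, which have two scheduled draws after each dose. It does not suit the vital-sign schedule.

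There is a smaller, related point about the incidence through 7 days. A reader of the report would take that label to mean a week of measurement, and the schedule does not provide one.

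**Working it through.** **Plan's own figure.** SAP 7.6.4 states no rate or precision for vital signs. The only quantitative design statement is in Protocol 3.6.4 and SAP 5.2: with 24 vaccinated per dose level, the chance of seeing at least one participant with an event is 92% at 10% incidence and 70.8% at 5%. Both reproduce: 1 − 0.90^24 = 92.0% and 1 − 0.95^24 = 70.8%. The same n = 24 is used below.

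**Step 1: count the scheduled readings after each dose** (Protocol Table 5 and 3.5.9; SAP 7.1 and Appendix A).

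| | After dose 1 | After dose 2 |
|---|---|---|
| Vital signs | Day 1 at ≥ 1 h; Day 29 pre-dose (2) | Day 29 at ≥ 1 h (1) |
| Vital signs within 7 days | Day 1 at ≥ 1 h (1) | Day 29 at ≥ 1 h (1) |
| Laboratory tests | Day 8; Day 29 (2) | Day 36; Day 57 (2) |

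The Day 29 pre-dose reading falls after dose 1, and the SAP 7.1 rule counts it from dose 1. Baseline is the last value before dose 1 for both vaccinations, so baseline adds no further imbalance.

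**Step 2: effect on a worst-value rate when nothing differs between doses.** Let p be the chance that a single reading is graded, the same at every reading. Then:

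- dose 2 rate = p
- dose 1 rate = 2p − P(both readings graded), which is 1 − (1 − p)² if the readings are independent

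For dependent readings, P(both) comes from a bivariate normal threshold model with correlation r. The documents give neither p nor r, so both are assumptions and are shown over a range. Cells give the dose 1 rate, with its ratio to p in brackets.

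| p (dose 2 rate) | r = 0 | r = 0.5 | r = 0.7 | r = 0.9 |
|---|---|---|---|---|
| 2% | 3.96% (1.98) | 3.66% (1.83) | 3.37% (1.69) | 2.84% (1.42) |
| 5% | 9.75% (1.95) | 8.78% (1.76) | 8.04% (1.61) | 6.81% (1.36) |
| 10% | 19.0% (1.90) | 16.8% (1.68) | 15.3% (1.53) | 13.1% (1.31) |
| 20% | 36.0% (1.80) | 31.3% (1.56) | 28.7% (1.44) | 25.0% (1.25) |

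At r = 0.999 the ratio is still 1.02 to 1.04. It reaches 1 only if the two readings always agree.

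**Step 3: in participants.** At p = 10% and n = 24, dose 2 is expected to show 24 × 0.10 = 2.40 participants. Dose 1 is expected to show 24 × 0.19 = 4.56 with independent readings, 4.02 at r = 0.5, 3.68 at r = 0.7 and 3.15 at r = 0.9. With independent readings, and treating the two dose counts as independent binomials, dose 1 shows more affected participants than dose 2 with probability 0.76 and fewer with probability 0.13.

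**Step 4: with one matched reading per dose.** Both rates equal p and the ratio is 1.00.

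**The case against.** The strongest reply is that no objective or endpoint asks for dose 1 against dose 2. The primary objective compares dose levels with placebo, vital signs are listed in SAP 4.1 among the other safety assessments, and escalation rests on blinded review of data through 7 days after the first vaccination. This stands as a limit on importance. It does not remove the point, because Protocol 3.6.6.2 requires graded vital signs to be analysed by vaccination, so the two columns are a planned display.

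A second reply is that the matched comparison already exists. It does for observed values and changes from baseline, which are summarised by visit with the 1-hour readings as separate rows. It does not exist for grades.

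A third is that SAP 7.6.4 never says which readings belong to which dose, and that the SAP 7.1 rule defines Study Day rather than eligibility for this table. That is fair: placing Day 29 pre-dose under dose 1 is an inference, though a natural one. The silence is itself a reason to specify.

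Equal risk at every reading is also a simplification. It is doubtful for temperature, since Protocol 3.4.2.3 treats fever at the visit as a reason not to vaccinate at that time, and Protocol Table 6 grades fever under systemic reactions.

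Four stronger readings are tempting, and the documents do not support them.

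- *Dose level against placebo is biased.* All groups share one schedule within each vaccination, so that contrast is not distorted by this imbalance. Pooled placebo carries the same two-to-one pattern.
- *Dose 1 must look worse.* The effect is an expectation under equal risk. A large true rise after dose 2 could outweigh it.
- *The incidence through 7 days uses only the 1-hour readings.* Those are the only scheduled ones. Protocol 3.5 allows unscheduled visits, and 3.5.9 calls for further assessments after a Grade 3 or higher value. Such readings could fall in the window, and SAP 7.6.4 does not exclude them.
- *The Grade 2 or higher incidence has the same two-to-one defect.* It is not split by vaccination. Restricting it to the 1-hour readings would discard possibly symptom-prompted values and make a safety count less conservative.

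**Conclusion.** The point holds for one display, the worst-grade vital-sign shift table compared between first and second vaccination. The count of two scheduled readings against one comes directly from the schedule, with the Day 29 pre-dose reading placed under dose 1 by the SAP 7.1 rule. Under equal per-reading risk, dose 1 is inflated in expectation. At an assumed 10% per reading the ratio runs from about 1.3 (correlation 0.9) to 1.9 (independent readings). Over 2% to 20% it runs from 1.25 to 1.98 for correlations from 0.9 down to 0. These sizes are illustrations because the documents give no rate or correlation; the direction needs only equal risk and readings that do not always agree.

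The 7-day incidence needs a labelling correction only: one scheduled reading falls in that window after each dose. No primary endpoint, sample size or placebo comparison is affected. It is worth correcting because safety is the primary objective and the change is nearly free.

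**What to change.** In SAP 7.6.4:

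1. Base the first-versus-second vaccination shift table on the scheduled reading at least 1 hour after each dose, one per dose.
2. Show the shift from baseline to the Day 29 pre-dose reading as its own time point.
3. Add a worst-value row or table that includes unscheduled readings, and say so explicitly, as SAP 7.6.3 does for laboratory tests, so that no signal is lost.
4. Keep the Grade 2 or higher incidence after any vaccination on all readings.
5. Footnote or relabel the incidence through 7 days to say that the only scheduled reading in the window is the one at least 1 hour post-dose, plus any unscheduled readings.

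The cost is SAP wording and table specifications, with an extra row or footnote in the output. No new data and no protocol amendment are needed.

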7.7 Immunogenicity Analysis

The GMT will be calculated by averaging the log-transformed titers and then transforming back to the original scale as in the following formulas:

$$10^{\left\{\sum_{i=1}^{n}log_{10}(t_i)\atop n\right\}} \text{ or } e^{\left\{\sum_{i=1}^{n}log_{e}(t_i)\atop n\right\}}$$

where $t_1, t_2, ..., t_n$ are *n* observed immunogenicity titers. The 95% Cis are also calculated on the log-transformed values and the transforming back to the original scale.

7.7.1 Immunogenicity Assessments

The following immunogenicity assessments will be performed: nAb against ZIKV by PRNT, nAb against ZIKV by additional neutralization assays (including microneutralization [MN] and reporter virus neutralization test [RVNT]), bAb against ZIKV by ELISA binding assay, and IgG and IgM antibodies against envelope- and NS1-based antigens by ELISA or equivalent methodology to flaviviruses.

All immunogenicity data will be presented in a data listing.

7.7.2 Analysis of nAb against ZIKV by PRNT

The nAb against ZIKV by PRNT will be summarized by treatment group and scheduled visit as follows:

• GMT of nAb against ZIKV at Day 1, Day 29, Day 57, Month 7, and Month 13 as measured by PRNT with corresponding 95% CIs.

Protocol mRNA-1893-P101

• GMT of nAb against ZIKV in initially flavivirus seronegative participants at Day 1, Day 29, Day 57, Month 7, and Month 13 as measured by PRNT with corresponding 95% CIs.

- GMT of nAb against ZIKV in initially flavivirus seropositive participants at Day 1, Day 29, Day 57, Month 7, and Month 13 as measured by PRNT with corresponding 95% CIs.
- Percentage of participants who seroconverted from Day 1 (baseline) to Day 29, from Day 1 to Day 57, from Day 1 to Month 7, and from Day 1 to Month 13.
- Proportion of initially seronegative participants with a seroresponse at Day 29, Day 57, Month 7, and Month 13 as measured by PRNT.
- Proportion of initially seropositive participants with a 2-fold or 4-fold increase in nAb titers as compared with baseline at Day 29, Day 57, Month 7, and Month 13 as measured by PRNT.
- Reverse cumulative distribution of nAb against ZIKV at Day 1, Day 29, Day 57, Month 7, and Month 13 as measured by PRNT.

7.7.3 Analysis of nAb against ZIKV by Microneutralization Assay and Reporter Virus Neutralization Test

The nAb against ZIKV as measured by MN and RVNT will be summarized by treatment group and scheduled visit as follows:

- GMT of nAb against ZIKV at Day 1, Day 29, Day 57, Month 7, and Month 13 as measured by MN and RVNT with corresponding 95% CIs.
- GMT of nAb against ZIKV in initially flavivirus seronegative participants at Day 1, Day 29, Day 57, Month 7, and Month 13 as measured by MN and RVNT with corresponding 95% CIs.
- GMT of nAb against ZIKV in initially flavivirus seropositive participants at Day 1, Day 29, Day 57, Month 7, and Month 13 as measured by MN and RVNT with corresponding 95% CIs.
- Percentage of participants who seroconverted from Day 1 (baseline) to Day 29, from Day 1 to Day 57, from Day 1 to Month 7, and from Day 1 to Month 13.
- Proportion of initially seronegative participants with a seroresponse at Day 29, Day 57, Month 7, and Month 13 as measured by MN and RVNT.

Proportion of initially seropositive participants with a 2-fold or 4-fold increase in nAb titers as compared with baseline at Day 29, Day 57, Month 7, and Month 13 as measured by MN and RVNT.

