1.6 Rationale for Study Design

The study is designed to generate the safety and immunogenicity data required to select the optimal dose of mRNA-1893 for further development in both endemic and nonendemic populations. Preclinical and clinical data support the expectation that a 2-dose vaccination schedule, 1 month apart, will induce a protective immune response. The 2-dose schedule will be explored at a range of doses in 2 subpopulations: endemic and nonendemic. The

nonendemic population will be represented by participants recruited from the general population who are flavivirus seronegative. The endemic population will be represented by participants recruited from endemic Zika regions who are seropositive for flavivirus (including dengue, West Nile, and Zika).

In order to explore vaccine safety, dosing will begin with 10 μg (Cohort 1) and escalate to 30, 100, and 250 μg. For each dose cohort, 5 flavivirus seronegative participants will be randomly assigned to dosing (4:1 mRNA-1893 to placebo) and followed for 7 days after the first vaccination, with safety oversight to confirm no pause rules were met (Section 3.4.2.2; Section 3.5.6) before randomly assigning the remaining 25 participants in the cohort. In addition, starting with the 10 μg-dose cohort, 7 days after all participants have received the first study vaccination, a blinded internal safety team (IST) will review all safety data for the cohort and determine the acceptability of escalating to the next mRNA-1893 dose level. The IST will approve escalation to the next higher dosing cohort after review of blinded safety data of the currently dosed cohort participants through 7 days after the first vaccination and any cumulative safety data of all cohorts as the trial advances.

Pause rules have been pre-established to trigger ad hoc unblinded Safety Monitoring Committee (SMC) reviews. The SMC is composed of independent experts with relevant expertise that will meet upon request of the IST, if required.

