Immunogenicity against ZIKV will be assessed before vaccination (baseline; Day 1) and 28 (+14) days after each vaccination and assessed for persistence at Month 7 and at Month 13 (12 months after the last vaccination) with assays that are relevant for the field, in particular, neutralization assays that may correlate with protection. A 12-month Long-Term Follow-up Phase after the last vaccine administration will be performed to assess if any serious AEs (SAEs), medically attended AEs (MAAEs), and AEs of special interest (AESIs) have occurred during the study. This is comparable to the assessments performed by the Sponsor across its mRNA vaccine candidates in early development.

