3.4 Study Dosing Groups

3.4.1 Method of Assigning Participants to Dosing Groups

Participants will be randomly assigned (Day 1) in a blinded manner using the centralized Interactive Response Technology (IRT), with approximately 30 participants assigned to each cohort. Study vaccine dosing will begin with Cohort 1 (10 µg mRNA-1893 or placebo), followed sequentially by Cohort 2 (30 µg mRNA-1893 or placebo), Cohort 3 (100 µg mRNA-1893 or placebo), and Cohort 4 (250 µg mRNA-1893 or placebo). Within each cohort, participants will be randomly assigned in a blinded manner to receive either mRNA-1893 vaccine or placebo (4:1 mRNA-1893 vaccine to placebo) using the centralized IRT. Participants will be stratified according to flavivirus baseline serostatus.

In each cohort, the initial 5 participants (all seronegative) will be randomly assigned to vaccine or placebo (4:1 mRNA-1893 vaccine to placebo) before the remaining participants (n=25, 20 seronegative and 5 seropositive) are enrolled in the cohort.

Randomization by the centralized IRT will be in accordance with pre-generated randomization schedules, with only the unblinded pharmacy personnel having controlled access.

Dose group assignment in each cohort and stratification within each cohort is summarized in Table 1.

Table 1: Dose Group Assignment

	Dose Group Assignment	n	Flavivirus Status Stratification ^a		Total
Cohort			Status	n	(Ratio)
	mRNA-1893 10 μg	24	+	4	
1			-	20	30
1	Placebo	6	+	1	(4:1)
			-	5	
	mRNA-1893 30 μg	24	+	4	
2			-	20	30
2	Placebo	6	+	1	(4:1)
			-	5	
	mRNA-1893 100 μg	24	+	4	30 (4:1)
3			-	20	
3	Placebo 6	6	+	1	
		0	-	5	
	mRNA-1893 250 μg 24	24	+	4	30 (4:1)
4		24	-	20	
4	Placebo	6	+	1	
			-	5	
			-	Total	120

Abbreviations: - = flavivirus seronegative; + = flavivirus seropositive.

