3.6.4 Sample Size Calculations

A total of 120 participants (30 participant per cohort) are planned for enrollment in the study and random assignment to study dosing. The sample size is considered sufficient to meet the study objective of identifying a dose and establishing initial safety results in a population of healthy adults in both endemic and nonendemic Zika regions. With 24 subjects receiving mRNA-1893 in each dose level, there is a 92% probability to observe at least 1 subject with an AE if the true incidence of the AE is 10% and a 70.8% probability if the true incidence of the AE is 5%.

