- d Serology testing will include hepatitis B virus surface antigen, hepatitis C virus antibody, human immunodeficiency virus type 1 and 2 antibodies.
- ^e Flavivirus screening by ELISA will include screening for dengue, West Nile, and Zika.
- f Urine drug screen will include amphetamines, benzodiazepines, cocaine, methadone, opiates, and phencyclidine (Exclusion Criterion 26, Section 3.2.2).
- g Urine pregnancy testing only for women of childbearing potential (performed at the local laboratory) at the Screening Visit, prior to vaccination administration and as needed at unscheduled visits.
- h Participants are assessed for eligibility/contraindications for second vaccination (Section 3.4.2.3).
- At each vaccination visit (Day 1 and Day 29), study staff will provide a diary card to participants and training on its proper use. The participant will use the diary card (Section 3.5.2) for recording information on solicited AEs (Section 3.5.6) during the 6 days after vaccine administration, unsolicited AEs (Section 3.5.7) during the 28 days after each vaccination.
- At each visit when vaccine injections are administered, participants will be monitored for 60 minutes after vaccine administration; assessments will include vital sign measurements and monitoring for local or systemic reactions.
- ^k For all participants, blood samples for immunogenicity testing will be collected for the analysis of vaccine-induced immunogenicity (Section 3.5.3). At EOS, blood samples will also be used to test for flavivirus seroconversion.
- Sample collection before study vaccination.
- m During the Vaccination Phase, all participants will receive a post-vaccination safety telephone call at 24 hours and 48 hours after vaccinations (Day 2 and Day 3 after first vaccination and Day 30 and Day 31 after second vaccination). Trained site personnel will inquire about the presence of solicited and unsolicited AEs and concomitant medication use and will remind participants to keep their diary cards up to date (Section 3.5.2).
- ⁿ The investigator must report all SAEs, MAAEs, and AESI within 24 hours of awareness (Section 3.5.7.3).

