6.2.2 Per-Protocol Sets

The PP sets for analysis of immunogenicity data will be defined for each visit (ie, Visit 1 - Day 1, Visit 5 - Day 29, Visit 9 - Day 57 [Month 2], Visit 14 - Month 7, Visit 20 - Month 13 [EOS] PP sets) and consist of all participants who meet the following criteria:

- Did not have a major protocol deviation
- Received vaccine within the acceptable vaccination window and received full dose[s] of assigned vaccine
- Had immunogenicity samples taken within acceptable visit windows
- Had a pre-vaccination and the corresponding 1 post-vaccination serum sample available for testing. For the Visit 1 – Day 1 PP set, participants will only be required to have a pre-vaccination serum sample available for testing

Protocol mRNA-1893-P101

Participants who miss the second vaccination may still be included in the PP set for Visit 5 immunogenicity data analysis. If the second vaccination occurs outside of the window, the subsequent data may need to be excluded from the PP set for visits occurring after the second vaccination.

In addition, an overall PP set will be defined for modeling across visits. A participant who is included in any one of the per-visit PP sets will be included in the overall PP set.

The PP sets will be used for the primary immunogenicity analyses at each interim analysis and at the final analysis.

7 Statistical Analysis

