7.7.5 Analysis of IgG and IgM antibodies against envelope- and NS1- based antigens

The GMC for IgG and IgM antibodies against envelope- and NS1-based antigens present in serum collected at baseline and at end of study measured as antibody binding by ELISA or equivalent methodology to flaviviruses will be summarized by treatment group with corresponding 95% CIs.

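### The Month 7 and Month 13 antibody summaries have no flag or sensitivity analysis for participants who acquire a flavivirus infection during follow-up, so persistence is overstated if an infection occurs and raises ZIKV antibody

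*SAP*

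**What the plan says.** Protocol 1.6 says that immunogenicity is "assessed for persistence at Month 7 and at Month 13 (12 months after the last vaccination"). The same section represents the endemic population by "participants recruited from endemic Zika regions who are seropositive for flavivirus". Protocol 2.3 makes flavivirus infection during the trial an exploratory objective. Table 5, footnote k, adds: "At EOS, blood samples will also be used to test for flavivirus seroconversion". Protocol 3.5.5 calls for dengue serology and PCR when a medically attended event suggests flavivirus infection.

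SAP 7.7.2 plans "GMT of nAb against ZIKV in initially flavivirus seropositive participants at Day 1" and at Day 29, Day 57, Month 7 and Month 13. It also plans the seronegative and overall GMTs, seroconversion, seroresponse, and 2- or 4-fold rises. SAP 7.7.3 and 7.7.4 repeat this for the microneutralization, reporter-virus and ELISA binding assays.

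The per-visit per-protocol sets (SAP 6.2.2) require that a participant "Did not have a major protocol deviation", was dosed fully and in window, was sampled in window, and has the serum needed. Infection is not listed. It is also absent from Protocol 3.4.8.2, which names the drugs, vaccines and blood products that may affect per-protocol evaluability. The ITT set (SAP 6.2.1) keeps everyone randomised. SAP 7.7.5 uses the envelope and NS1 IgG and IgM data, "present in serum collected at baseline and at end of study", only as group geometric means. It does not define an infected participant.

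**The concern.** The secondary objective is the immunogenicity of the vaccine. A late titre in someone infected after vaccination may reflect vaccine, infection or both, and the plan cannot tell these apart in its summaries. The protocol guards against other outside sources of antibody: earlier flavivirus vaccination is an exclusion criterion, and immunoglobulins or other vaccines can affect per-protocol evaluability. Its primate data (Protocol 1.2) also show that ZIKV infection alone can produce the measured outcome, since buffer-control animals had neutralizing titres only after challenge.

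Two readings are at stake: how long antibody lasts, and how seropositive and seronegative participants compare, which Protocol 1.4 gives as a purpose of the study. The seropositive groups are the smallest and are recruited in endemic regions. One infection there could make a waned response look sustained. If an infection is found and no rule exists, any rule would be chosen after the titres have been seen.

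**Working it through.** **Inputs.** After the first 5 seronegative participants, each cohort enrols "n=25, 20 seronegative and 5 seropositive" (Protocol 3.4.1). At 4:1, Table 1 gives 4 seropositive and 20 seronegative vaccinees per dose, so 24 in all. There are 16 seropositive vaccinees over four doses and 4 seropositive placebo recipients when placebo is pooled. The infection rate r and boost k are not in the documents; the values below are assumptions.

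**The plan's own figure.** Protocol 3.6.4 states: "With 24 subjects receiving mRNA-1893 in each dose level, there is a 92% probability to observe at least 1 subject with an AE" at a true incidence of 10%, and 70.8% at 5%. The formula 1 − (1 − p)^24 gives 1 − 0.90^24 = 0.920 and 1 − 0.95^24 = 0.708. Both reproduce. No figure is given for infection or persistence.

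**Effect on a GMT.** The GMT is the back-transformed mean of log titres (SAP 7.7). Multiplying one of n titres by k adds log(k)/n to that mean, so the GMT is multiplied by k^(1/n).

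| Assumed boost k | n = 4 | n = 24 |
|---|---|---|
| 2 | 1.19 | 1.03 |
| 4 | 1.41 | 1.06 |
| 16 | 2.00 | 1.12 |

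Among the 20 seronegatives, k = 4 gives 4^(1/20) = 1.07.

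**Effect on apparent waning.** Suppose the true GMT of a group of 4 falls 4-fold after Day 57 (assumed). One 4-fold boost gives 0.25 × 1.41 = 0.35, seen as a 2.8-fold fall. One 16-fold boost gives 0.25 × 2.00 = 0.50, seen as a 2-fold fall.

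**Effect on a responder rate.** One participant in 4 is 25 points. Moving from 0/4 to 1/4 changes the Clopper-Pearson 95% interval (the method in SAP 7.1) from 0-60.2% to 0.6-80.6%.

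**Chance that it arises.** With independent infections at a common rate r over follow-up, the chance of at least one is 1 − (1 − r)^n.

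| Assumed r | 4 seropositive vaccinees at one dose | 16 over all doses |
|---|---|---|
| 1% | 3.9% | 14.9% |
| 2% | 7.8% | 27.6% |
| 5% | 18.5% | 56.0% |
| 10% | 34.4% | 81.5% |

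**Is there a rule elsewhere?** SAP 7.4 defines a deviation as a departure from approved procedures, which an infection is not. Major deviations are classified in a separate review plan that is not among the documents, but on that definition it is unlikely to cover infection.

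**The case against.** The strongest reply is that the harm is conditional and the main effect small. No infection rate or boost is given. The flaviviruses screened for are dengue, West Nile and Zika, and nothing in the documents says that the first two raise ZIKV titres. For Zika itself, vaccinated macaques had no or only sporadic low-level viral RNA after challenge, so a boost in vaccinees may be smaller than in the unvaccinated. In all 24 vaccinees at a dose, a 4-fold boost in one moves the GMT by 6%. Groups of 4 are imprecise for any reason, as the intervals show. All immunogenicity data will be listed, so a late rise alongside an NS1 rise could be spotted. Summarising titres whatever their source is also a legitimate descriptive choice in a Phase 1 trial with safety as its primary endpoints.

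These points limit the size of the concern. They do not supply a rule, and a listing is not an analysis.

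A reader might infer more than the documents support:

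- **That infection could change dose selection.** The analyses said to inform that choice are the cohort locks through 28 days after dose 2 (Protocol 3.6.8; unblinding in 3.4.5), before the Month 7 and Month 13 visits.
- **That an infected placebo recipient biases a comparison.** SAP 7.7 plans summaries by group with intervals, and no between-group contrast. Such a case would instead help show background infection, although pooled placebo has only 4 seropositives.
- **That every infection raises ZIKV titres regardless of vaccination.** The documents do not establish this.

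**Conclusion.** The gap is real. The plan anticipates infection and collects serum to detect it, but never uses the result when late titres are summarised as persistence. The bias is upward if an infection occurs and raises ZIKV antibody, and zero if none occurs. Under the assumed 2- to 16-fold boost, one case inflates the GMT 1.19 to 2.0 times in a seropositive dose group and 1.03 to 1.12 times across all 24 vaccinees at a dose. It can move a seropositive responder rate by 25 points.

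The consequence is confined to the final descriptions of persistence and of the difference between serostatus groups. This is a cheap improvement worth making before the final analysis, not a defect in the primary safety analysis or the Day 57 interims. That the gap exists is certain from the text; how much it matters depends on an infection rate and boost that the documents leave open.

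**What to change.** In SAP 7.7.2-7.7.4, add a supportive sensitivity analysis that repeats the Month 7 and Month 13 GMT/GMC, seroconversion, seroresponse and 2-/4-fold summaries without titres collected after evidence of infection.

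- **Evidence, defined before the final unblinding:** an anti-NS1 rise from baseline by the assay's own cut-off, or a positive dengue PCR or serology from the work-up of a medically attended event. NS1 is suitable because the vaccine encodes only prME, so an envelope response cannot separate infection from vaccination. A rise is needed because seropositives may already have NS1 antibody. The work-up covers dengue only and should not be treated as a general flavivirus test.
- **Timing:** Protocol Table 4 lists 5 collections for the envelope/NS1 assay, whereas SAP 7.7.5 reports baseline and end of study only. If Month 7 serum is tested, use it to date the infection. If not, apply the exclusion at both visits and say so.
- **Reporting:** keep the per-protocol analysis as the main result, show both side by side, and list infected participants by treatment group (including placebo) and serostatus.

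The cost is SAP wording and a re-run of existing tables; no new blood draw is needed. Two downsides should be stated. Numbers fall slightly, to as few as 3 in a seropositive group. The exclusion also conditions on a post-randomisation event that vaccination may affect: if participants with low titres are infected more often, removing them raises the remaining GMT. The result is therefore supportive only and should not replace the main one.
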